10 MONITORING

10.1 Monitoring Plan

Sponsor monitoring responsibilities will be provided by the CRO. Individuals qualified by education, training, and experience will be assigned to monitor the study. The study monitors will periodically contact the site and perform on-site visits.

The CRO will assign qualified blinded monitor(s) and unblinded monitors to visit the site (including all field sites) during the study period. The extent, nature, and frequency of visits will be based on such considerations as study objectives, study design and complexity, and enrollment rate. Periodicity and nature of monitoring activities will be described in the Monitoring Plan that will be approved by POLYVAC and PATH in advance of monitoring. The monitoring activities will be done according to the CRO's SOPs with the goals to protect the rights, safety and wellbeing of study participants; and assure the study compliance, data quality and integrity. The Monitoring Plan will contain detailed report requirements and study progress for POLYVAC and PATH. Representatives of POLYVAC and PATH or designates may participate in monitoring visits or visit the study site on their own in order to provide proper oversight.

10.2 Initiation Visit

The study monitor/PATH will contact the site prior to the start of the study to discuss the protocol and data collection procedures with site personnel. Prior to enrollment of participants at the study site, specific regulatory documents must be available. These include approvals from the independent ethics committee (IEC) at the Vietnam Ministry of Health and from institutional review boards of the participating institutions. Curriculum vitae for key investigators must also be available. POLYVAC/ PATH will inform the investigator of any additional documents that need to be provided.

10.3 Routine Monitoring Visits

Monitoring will be conducted according to an agreed upon Site Monitoring Plan. Monitoring will be targeted towards issues critical to the rights and welfare of study participants as well as accuracy and integrity of the study data. Individuals responsible for monitoring the study should have access to all records needed in order to periodically ensure the ethical and safe conduct of the study and the integrity/validity of the recorded data.

During sites visits and contacts, the monitor will:

- 1. Assess if consent was properly obtained.
- 2. Assess adherence to the protocol eligibility criteria.
- 3. Look for evidence that randomization was followed.
- 4. Look for evidence that blinding was maintained.
- 5. Look for evidence that the product was administered correctly.
- 6. Check on study conduct and documentation of procedures/assessments related to the study endpoints:
 - Specimens obtained correctly.
 - Specimens labeled correctly.
 - Reactogenicity diaries completed and collected.
- 7. Check on study conduct and documentation of protocol-required safety assessments, including SAEs.
- 8. Ensure that there is documentation of withdrawals and deaths with reasons provided.

The blinded monitor(s) will be responsible for all aspects of the clinical trial related to subjects, the blinded site staff, and regulatory and audit readiness and its documentation. The CRO will also assign an unblinded study monitor, who will visit the site (including all field sites) during the study period to assess and verify activities of the unblinded site personnel including review of treatment assignments, vaccine storage and accountability, and dosing-related matters and their documentation. Both blinded and unblinded study monitors will provide a blinded report to the CRO and Sponsor/PATH of ongoing activities and issues requiring resolution. Any unblinding of additional project team personnel required to resolve issues will be clearly documented in the TMF. Of note, all reports to blinded personnel by the unblinded CRO monitor will be constructed in order to maintain the blind during the trial. No report that would break the blind will be released into the TMF until after database lock.

As part of study conduct, the Principal Investigator will have to agree to allow the monitor direct access to all relevant documents and to allocate his/her time and the time of his/her staff to discuss findings and relevant issues. The study consent also makes participants aware that medical records relevant to events in the study may be accessed and viewed by people conducting and overseeing the study.

The Principal Investigator also agrees to allow representatives of POLYVAC and PATH or its designates to occasionally accompany the monitor during site visits.

10.4 Close-out Visit

Upon completion of the study, the study monitor and the investigator will conduct the following activities:

- Data clarification and/or resolution.
- Accounting, reconciliation, and destruction (if planned) at sites of used and unused vaccines.
- Review of site study records for completeness.
- Return of all study data to POLYVAC.

11 AUDITS AND INSPECTIONS

For the purpose of compliance with applicable regulatory guidelines, it might be necessary for POLYVAC, it's designates, or national or foreign regulatory authorities to conduct a site audit/inspection. This could occur at any time from site initiation to after conclusion of the study. If a regulatory authority requests an inspection, the Principal Investigator must inform POLYVAC and PATH immediately about this request.

The Principal Investigator should agree to allow the auditor/inspector to have direct access to all relevant documents and to allocate his/her time and the time of his/her staff to the auditor/inspector to discuss findings and any relevant issues.

12 STATISTICAL CONSIDERATIONS

12.1 Overview and General Considerations

An outline of the planned statistical analyses is provided in the following sections. Prior to a database lock, a statistical analysis plan (SAP) that contains full details of all planned analyses will be created and finalized. All statistical analyses will be performed using SAS[®] software version 9.4 or later.

12.2 Sample Size and Power Considerations

The sample size for the study is determined based on the regulatory requirement to submit safety data for 500 vaccine recipients receiving the new vaccine. Considering a dropout rate of 10% the study will enroll 825 infants receiving vaccines at the ratio of 2:1 (550 participants receiving the liquid formulation of ROTAVIN and 275 participants receiving the frozen formulation ROTAVIN-M1).

The non-inferiority of the liquid formulation of ROTAVIN to currently licensed frozen formulation of the vaccine (ROTAVIN-M1) will be primarily assessed by GMC of serum antirotavirus IgA antibody concentrations 28 days after the second vaccination in all participants enrolled at one of the two study sites.

It is anticipated that at least 375 infants (250 ROTAVIN recipients and 125 ROTAVIN-M1 recipients) at one of the two sites will provide evaluable blood samples. Considering a non-evaluability rate of approximately 15%, at least 450 participants will be enrolled at this centre. Power to show that the ratio of the GMC in the liquid formulation of ROTAVIN group to that in the ROTAVIN-M1 group is at least 0.5 was calculated using a one-sided two-sample t-test with a significance level of 0.025. Table 12.1 shows the power corresponding to different sizes of evaluable participants and assumed standard deviations (SD) of log10-transformed IgA concentrations.

Table 12.1: Power to detect at least a ratio > 0.5 of anti-rotavirus IgA GMCs between ROTAVIN liquid formulation and ROTAVIN-M1 groups 28 days after the second dose, based on various group sizes and different assumed SD of log10 IgA antibody concentrations

Assumed SD of log10 IgA antibody concentrations	Number of evaluable participants per group (ROTAVIN liquid formulation vs. ROTAVIN-M1)	Power to detect at least a 0.5 ratio of anti-rotavirus IgA GMCs between ROTAVIN liquid formulation and ROTAVIN-M1
0.70	250 vs. 125	97%
0.75	250 vs. 125	95%
0.80	250 vs. 125	93%

With 250 evaluable participants in the liquid formulation group and 125 evaluable participants in ROTAVIN-M1 group and an assumed SD of the log10 IgA antibody concentrations of 0.8 which was estimated from a phase 3 clinical trial for ROTAVIN-M1 conducted in Vietnam, we will have 93% power to demonstrate the non-inferiority of ROTAVIN liquid formulation to ROTAVIN-M1 in terms of GMC using a one-sided two-sample t-test with a non-inferiority margin of 0.5 and a significance level of 0.025.

With the proposed sample size of 550 participants receiving the liquid formulation of ROTAVIN, this study is designed to have 95% power to detect at least one solicited post-vaccination reaction after each vaccination if true incidence is 0.55%.

The percentage of participants with at least one solicited post-vaccination reaction will be compared between the two vaccine groups after each vaccination. The minimum difference in percentage of participants with a solicited post-vaccination reaction between ROTAVIN liquid formulation and ROTAVIN-M1 groups that can be detected with 90% power is provided in Table 12.2, based on a two-sided Fisher's Exact test with a significance level of 0.05.

Table 12.2: The minimum difference in percentage of participants with solicited postvaccination reaction after each vaccination between ROTAVIN liquid formulation and ROTAVIN-M1 groups can be detected with 90% power

Expected percentage of participants with a solicited post-vaccination reaction in ROTAVIN-M1 group	Number of vaccinated participants per group (ROTAVIN liquid formulation vs. ROTAVIN- M1)	Minimum difference in percentage of participants with a solicited post- vaccination reaction between the groups which can be detected with 90% power
1%	550 vs. 275	4.2%
2%	550 vs. 275	5.1%
5%	550 vs. 275	6.8%
10%	550 vs. 275	8.6%
15%	550 vs. 275	9.8%
20%	550 vs. 275	10.6%

With 550 vaccinated participants in ROTAVIN liquid formulation group and 275 vaccinated participants in ROTAVIN-M1 group, the study has 90% power to detect at least a 6.8% difference in percentage of participants with solicited post-vaccination reaction between the ROTAVIN liquid formulation and ROTAVIN-M1 groups after each vaccination, assuming that the rate of the solicited reactogenicity is 5% in the ROTAVIN-M1 group and a significance level of 0.05.

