Site		Vaccine		Placebo	
		Pre- vaccination	Post-vaccination	Pre- vaccination	Post- vaccination
Phu	n	300	255	99	81
Tho	GMC (95% CI)	6.0 (5.6 - 6.4)	68.2 (55.8 - 83.2)	5.9 (5.2 – 6.7)	7.7 (5.9 - 10.1)
Thai	n	300	248	100	92
Binh	GMC (95% CI)	5.5 (5.2 - 5.7)	109.1 (89.3 - 133.3)	5.2 (5.0 - 5.5)	8.2 (6.5 – 10.2)
Total	n	600	503	199	173
	GMC(95% CI)	5.72 (5.5-5.9)	85.9 (74.5-99.1)	5.6 (5.2-6.0)	8.0 (6.7-9.4)

 Table 2.11: IgA Geometric Mean Concentration (GMC) before and after the administration of vaccine/placebo at study sites

Another approach to evaluate the immunogenicity of vaccine was to study the distribution of antibody concentrations. The vaccine induced IgA antibody concentration at 80 or higher in 65.8% of children in Thai Binh and 54.5% in Thanh Son, Phu Tho. Meanwhile, there were still 6.5% of children in Thai Binh and 10.6% in Phu Tho with low antibody levels [20-40], and 14.1% of children in Thai Binh and 20% in Phu Tho did not induce IgA antibody response (<20). A small number of children in the placebo group also induced the concentration levels of 20-640, presumably due to a natural infection.

IgG response

Before participating in the study, the RV-IgG was detected in children enrolled in the study (100% in Thai Binh and Thanh Son). The persistence level of maternal antibody was quite high, approximately 320-5120 (accounting for 91.3-92.6% of samples). There were some samples with the antibody concentration of 10240 or higher (0.36-2.4%) (Table 2.12). Also, the geometric mean IgG antibody concentration before participating in the study of children in Thanh Son was higher than that of children in Thai Binh (p < 0.01).

Indicator	Thai Binh	Phu Tho	
n	285	205	
GMC	1175*	1521	
IgG concentration level			
<20	0.0%	0.5%	
[20-320)	5.6%	3.9%	
[320-10240)	92.6%	91.3%	
>=10240	1.8%	4.3%	

Table 2.12: Comparison of IgG antibody concentration levels of children be	fore
administration of vaccine/placebo in two study sites	

* Significant difference (p<0.01)

In this study, the IgG-GMC of the placebo group decreased 7.6 times in Thai Binh and 8.7 times in Phu Tho. This was consistent with the nature of IgG half-life of 3-4 weeks. Meanwhile, the IgG-GMC of the vaccine group increased 2.1 times in Thai Binh, or decreased (but not significantly in Thanh Son-Phu Tho (Table 2.13), showing that the vaccine enabled to induce the IgG immune responses even when the pre-administration antibody level was high.

Site	IgG	Placebo		Vaccine		

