7.4 Early Termination

Participant parents/LARs have the right to decline study treatment or procedures for any reason and at any time during the study. If a participant parent/LAR declines further vaccination or study procedures (but continues in the study for safety assessment) this will be recorded as a study deviation and the reason will be clearly documented in the source document. The participant parent/LAR will be encouraged to have their child complete the remaining applicable safetyrelated follow-ups. A blood sample will not be collected in infants who miss one of the vaccinations. If the participant parent/LAR does not wish to remain in the study by declining any follow-ups or procedures, the participant parent/LAR can choose to withdraw consent and be withdrawn from the study.

The participants may be withdrawn from the study for any of the following reasons:

- If parent/LAR of participant wishes to withdraw consent.
- If the Principal Investigator (PI) decides that withdrawal is in the best interest of the participant.
- Significant non-compliance with treatment regimen or trial requirements.
- Participant is lost to follow-up.
- The sponsor/manufacturer recommends to terminate the study.
- Governing IRBs recommends to terminate the study.

In all cases, where the participant is withdrawn from the study the reason for withdrawal will be documented in an appropriate section of the eCRF. However, the data collected up to the last contact will be part of the analysis. In the event of withdrawal from study, reasonable efforts should be made to conduct the following procedures:

- Review diary card if still in use prior to withdrawal.
- Updating any ongoing AE/SAEs that remain ongoing at time of participant's last visit prior to withdrawal.
- Query about AEs, SAEs and concomitant medications since the last visit.
- Conduct physical examination.
- Update contact information.

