12.3.4 Safety population

The safety population is defined as all participants in the enrolled population who received a study vaccination and had any safety data available. Participants in the safety population will be analyzed as "treated", i.e. according to the actual vaccine received at the first dose. All safety analyses will be performed using this population. The denominators for different safety endpoints may vary according to the number of participants with available data for the specific endpoint. For instance, the solicited systemic adverse event endpoints will be based only on those who have the corresponding CRF data regardless of other safety follow-up data.

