12.4.5 Handling of Dropouts and Missing Data

Missing immunogenicity data will not be imputed and will be analyzed as if they were missing randomly.

Over the whole study period, the number and percentage of participants who withdraw from the study will be provided by vaccine group. All withdrawn participant's post-randomization will be further described regarding their time to dropout and their reasons for withdrawal. For participants who withdraw from the study, their data collected before withdrawal will be analyzed under full analysis (FA) population and safety population when applicable.

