4.3.4 Concomitant Medications/Treatment

Childhood vaccines as per the EPI of the Government of Vietnam [Diphtheria, Tetanus, Pertussis, Haemophilus influenzae type B and Hepatitis B vaccine (DTwPHib-HepB) and Oral Polio Vaccine (OPV)] and Pneumococcal vaccines will be allowed during the study period, but they should not be administered within 7 days before or after study vaccine administration. This is required to avoid any overlap of safety event due to study vaccine and EPI vaccines. The study participants may receive additional doses of OPV as required during special immunization rounds irrespective of the timing of study vaccine.

5. Sample Size Considerations

The sample size for the study was determined based on the regulatory requirement to submit safety data for 500 vaccine recipients receiving the new vaccine. Considering a dropout rate of 10% the study will enroll 825 infants receiving vaccines at the ratio of 2:1 (550 participants receiving the liquid formulation of ROTAVIN and 275 participants receiving the frozen formulation ROTAVIN-M1[®]).

Immunogenicity will be assessed in participants enrolled from Quang Ninh site. It is anticipated that at least 375 infants (250 ROTAVIN recipients and 125 ROTAVIN-M1[®] recipients) will provide evaluable blood samples. Considering a non-evaluability rate of approximately 15%, at least 450 participants will be enrolled at this site.

Power to show that the ratio of the GMC in the liquid formulation is ROTAVIN group to that in the ROTAVIN-M1® group is at least 0.5 was calculated using a one-sided two-sample t-test with a significance level of 0.025. With 250 evaluable participants in the liquid formulation group and 125 evaluable participants in ROTAVIN-M1® group and an assumed SD of the log10 IgA antibody concentrations of 0.8 which was estimated from a phase 3 clinical trial for ROTAVIND-M1 conducted in Vietnam, we will have 93% power to demonstrate the non-inferiority of ROTAVIN liquid formulation to ROTAVIN-M1® in terms of GMC using a one-sided two-sample t-test with a non-inferiority margin of 0.5 and a significance level of 0.025.

With the proposed sample size of 550 participants receiving the liquid formulation of ROTAVIN, this study is designed to have 95% power to detect at least one solicited post-vaccination reaction after each vaccination if true incidence is 0.55%.

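### The planning SD of 0.8 is credited to a phase 3 trial whose own table implies about 0.71, and 550 infants cover the 500-recipient floor only up to 9.1% dropout, not 10% (minor)

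*Protocol*

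**What the plan says.** **SD.** Protocol 12.2 plans the non-inferiority comparison of GMCs as a one-sided two-sample t-test at 0.025 with a margin of 0.5. It uses 250 and 125 evaluable infants. The spread is described in these words: "assumed SD of the log10 IgA antibody concentrations of 0.8 which was estimated from a phase 3 clinical trial for ROTAVIN-M1 conducted in Vietnam". The stated power is 93%. Table 12.1 also prints 97% at SD 0.70 and 95% at SD 0.75. SAP section 5 repeats that the 0.8 was "estimated from a phase 3 clinical trial for ROTAVIND-M1 conducted in Vietnam" (the product name is misspelt there).

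The phase 3 immunogenicity results are in Protocol 2.5.3, Table 2.11. The post-vaccination total for vaccine recipients is "85.9 (74.5-99.1", with n = 503.

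**Dropout.** Protocol 12.2 and SAP section 5 both derive the total size from the "regulatory requirement to submit safety data for 500 vaccine recipients receiving the new vaccine". The protocol continues: "Considering a dropout rate of 10% the study will enroll 825 infants receiving vaccines at the ratio of 2:1", which gives 550 in the liquid arm and 275 in the frozen arm.

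Three other places bear on who counts. Protocol 12.3.4 defines the safety population as "all participants in the enrolled population who received a study vaccination and had any safety data available". Protocol 12.4.5 says of withdrawn infants that "their data collected before withdrawal will be analyzed under full analysis (FA) population and safety population when applicable". Protocol 5.2.1 lets the sponsor randomize additional infants for any who are randomized but never vaccinated.

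**The concern.** Both statements justify a number with an input that the protocol's own figures do not bear out.

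The t-test needs the SD within a vaccinated group, because both arms of this trial receive vaccine. A reader who goes to the cited phase 3 trial and works back from its confidence interval does not recover 0.8. Had the true value been larger than the assumed one, the power claim would have been at risk. The gap runs the other way, so what is at stake is whether the stated source is accurate.

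For the safety number, the stated allowance should leave at least the required 500. Multiplying 500 by 1.10 does not achieve that at 10% loss; dividing by 0.90 would. Since the section says this requirement determines the total sample size, the rationale should be arithmetically true.

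**Working it through.** **1. The plan's power figures.** Inputs from Protocol 12.2: margin log10(2) = 0.30103, one-sided alpha 0.025, n = 250 and 125, so df = 373. A true GMC ratio of 1 is assumed here; the documents do not state it. The standard error is SD x sqrt(1/250 + 1/125) = SD x 0.1095, and power comes from the noncentral t distribution with noncentrality 0.30103/SE.

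| SD | Power recomputed | Stated |
|---|---|---|
| 0.70 | 97.5% | 97% |
| 0.75 | 95.5% | 95% |
| 0.80 | 92.9% | 93% |

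Table 12.1 reproduces. The power calculation is sound; only the origin of the SD is in question.

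**2. The SD implied by Table 2.11.** SD = [log10(upper) - log10(lower)] / (2 x t) x sqrt(n), with t the 97.5% point on n - 1 df.

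- Vaccine, total: log10(99.1/74.5) / (2 x 1.965) x sqrt(503) = **0.707** (0.709 with 1.96). Moving each limit by 0.05 for rounding gives 0.704 to 0.710.
- Vaccine, Phu Tho (55.8 to 83.2, n = 255): 0.703.
- Vaccine, Thai Binh (89.3 to 133.3, n = 248): 0.696.

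Assuming normality on the log scale, the 95% confidence interval for the total SD is about 0.67 to 0.75, which excludes 0.8. Conversely, an SD of 0.8 with n = 503 would have printed 73.1 to 100.9 around 85.9.

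**3. Power at the implied SD.** At 0.707 it is 97.2% and at 0.71 it is 97.1%, against 92.9% at 0.80.

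**4. One possible origin of 0.8.** The placebo total in Table 2.11 (8.0, 6.7 to 9.4, n = 173) gives an SD of 0.490. Treating all 676 samples as one group:

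sqrt{[502 x 0.707² + 172 x 0.490² + (503 x 173/676) x (log10(85.9/8.0))²] / 675} = **0.797** (0.792 to 0.803 with rounding).

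This matches 0.8, but the documents neither confirm nor exclude it. If it was done, the vaccine-placebo difference was counted as within-group spread, which is the wrong SD for two vaccinated arms.

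**5. Dropout allowance.**

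- 500 x 1.10 = 550, the planned figure.
- 550 x 0.90 = 495, five below the floor.
- 500/0.90 = 555.6, so 556 would be needed at 10%.
- Break-even: 50/550 = 9.1%.

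The 9.1% is break-even in expectation only. If infants drop out independently, the chance that at least 500 of 550 remain is 26% at 10% dropout and 54% at 9.1%.

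The immunogenicity allowance in the same section does hold: 450 x 0.85 = 382.5, above the 375 needed.

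**The case against.** **Nothing depends on the SD.** The total of 825 is set by the safety requirement, and Table 12.1 already shows 97% at SD 0.70. This is correct, and it is why the point is minor.

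**Table 2.11 may not be the source.** The sponsor may have used individual data, another analysis set or another treatment of values below the limit. That cannot be excluded. But no other ROTAVIN-M1 phase 3 trial is described, so the origin of 0.8 should be given. The merged vaccine-placebo figure remains a conjecture.

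**The phase 3 SD may not carry over.** This trial takes blood in Quang Ninh, vaccinates at 60-91 days rather than 6-12 weeks, and uses a standard-curve ELISA reporting IU/ml. The phase 3 values carry no units and are described in doubling bands. About 14% and 20% of phase 3 vaccine recipients in the two provinces were below 20, so an assay's lower limit could affect the SD. These are good reasons to plan with a larger value. They do not make 0.8 an estimate from data that show 0.71, and the text does not present it as a deliberate margin. They also mean that 97% is the power if the phase 3 SD applies, not a prediction.

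**Later dropout hardly reduces the 500.** The requirement concerns recipients with safety data, and every vaccinated infant is observed for 30 minutes on Day 1. This largely stands: the floor is probably met. It also means that the dropout allowance, as the plan words it, is not what protects the floor.

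**Restating the allowance as 9% fits a rate to a chosen number.** This is fair. Saying whom the 500 counts is the better option, if the sponsor can confirm how the requirement counts; the documents do not spell that out.

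**Conclusion.** Both points hold as minor corrections.

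- **SD:** the stated phase 3 source supports about 0.71 for vaccine recipients, not 0.8. Power is understated by about four percentage points (93% against 97%). This rests on the Table 2.11 intervals being ordinary t- or z-based intervals for the mean of the log concentrations, and on that trial being the one meant.
- **Dropout:** the stated 10% allowance falls five infants short (495 against 500). The practical effect is probably nil under the plan's safety-population definition.

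The primary non-inferiority test, its margin and its power claim are not affected.

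**What to change.** Amend one or two sentences in Protocol 12.2 and the same text in SAP section 5.

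- **SD:** state that Table 2.11 implies about 0.71 in vaccine recipients, with about 97% power if that value applies here. Then either present 0.8 (93% power) as a deliberately larger assumption, or name its actual source and say whether placebo recipients were included.
- **Dropout:** either state that the 500 counts recipients of at least one dose with safety data, and drop the dropout justification, or restate the allowance as about 9%.

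The cost is wording only. Enrolment, analyses and the 93% claim stay as they are.

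### The 90% and 95% safety power figures are computed at 550/275 but stated for both doses; after Dose 2 they take no account of the plan's own 10% dropout, which could lower them to about 87% and 93.5%

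*Protocol*

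**What the plan says.** Protocol 12.2 sets the sample size from the "regulatory requirement to submit safety data for 500 vaccine recipients receiving the new vaccine". It continues: "Considering a dropout rate of 10% the study will enroll 825 infants", split as "550 participants receiving the liquid formulation of ROTAVIN and 275 participants receiving the frozen formulation ROTAVIN-M1".

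Two safety power statements follow.

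- **Detection in the liquid arm:** "95% power to detect at least one solicited post-vaccination reaction after each vaccination if true incidence is 0.55"%, based on all 550 infants.
- **Comparison between arms:** the text takes 550 and 275 vaccinated infants and states that "the study has 90% power to detect at least a 6.8% difference" between the arms; this is worked out "assuming that the rate of the solicited reactogenicity is 5% in the ROTAVIN-M1 group". Table 12.2 gives the same kind of figure for comparator rates from 1% to 20%, "based on a two-sided Fisher's Exact test with a significance level of 0.05". Every row uses 550 vs. 275. Both the table title and the sentence apply the result to each vaccination.

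SAP section 5 repeats both statements without a dropout adjustment.

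Four other provisions bear on the point.

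- Protocol 7.4: infants who discontinue after enrollment are not replaced, and loss is expected to be low.
- Protocol 12.3.4 and SAP 7.1: solicited endpoints count only infants whose CRF data for that endpoint exist.
- Protocol 12.4.2: the Fisher comparison is made after each vaccination.
- SAP 12.2: the any-dose table (Table 16) comes first, and the per-dose tables (17 and 18) are classed as supportive.

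**The concern.** The section allows for 10% dropout when it sets enrollment, then computes all its safety power on the undiminished 550 and 275. For Dose 1 that is reasonable. For Dose 2 the denominators can only shrink, because discontinued infants are not replaced and an infant without Dose 2 diary data is not counted. The same section treats immunogenicity differently: at least 450 infants are enrolled at the blood-sampling site, about 15% are assumed non-evaluable, and power is computed on 250 vs. 125. The safety figures have no such step.

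At stake is how a non-significant Dose 2 comparison is read. A reader would take it that a 6.8-point difference had a 90% chance of detection, when under the plan's own dropout assumption the chance may be somewhat lower.

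**Working it through.** **Inputs.** From Protocol 12.2: 550 and 275 infants; two-sided Fisher's exact test at 0.05; comparator rate 5%; difference 6.8 points, so 11.8% in the liquid arm; detection incidence 0.55%; dropout 10%. The timing of dropout is not given, so it is varied below.

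**Methods.** Comparison: exact power of the Fisher test, summing the binomial probabilities of all outcome pairs with p ≤ 0.05. Detection: P(at least one) = 1 − (1 − 0.0055)^n.

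**Step 1: reproduce the stated figures at 550/275.**

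- Fisher power, 11.8% vs. 5%: 90.8% (stated 90%).
- The six Table 12.2 rows: 90.7% to 91.0%.
- Detection: 1 − 0.9945^550 = 95.2% (stated 95%).

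The stated figures are correct for these denominators, and slightly conservative.

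**Step 2: Dose 2 denominators.** If the full 10% is lost before the Dose 2 diary: 550 × 0.9 = 495 and 275 × 0.9 = 247.5, taken as 248. The section's own target of 500 liquid recipients, at 2:1, gives 500/250.

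| Loss before Dose 2 diary | Liquid / frozen | Power, 6.8 points at 5% | P(at least one) at 0.55% |
|---|---|---|---|
| None | 550 / 275 | 90.8% | 95.2% |
| 2% | 539 / 270 | 90.1% | 94.9% |
| 3% | 533 / 267 | 89.7% | 94.7% |
| 5% | 522 / 261 | 89.1% | 94.4% |
| To the 500 target | 500 / 250 | 87.5% | 93.7% |
| 10% | 495 / 248 | 87.1% | 93.5% |

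The detection statement has little slack. It needs n ≥ ln(0.05)/ln(0.9945) = 543.2, so 544 infants; it falls below 95% once more than 6 of the 550 are missing.

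**Step 3: what 495/248 does support.**

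| Comparator rate | Stated difference | Power at 495/248 | Difference with 90% power at 495/248 |
|---|---|---|---|
| 1% | 4.2 | 88.2% | 4.35 |
| 2% | 5.1 | 87.6% | 5.35 |
| 5% | 6.8 | 87.1% | 7.16 |
| 10% | 8.6 | 87.5% | 9.00 |
| 15% | 9.8 | 87.3% | 10.27 |
| 20% | 10.6 | 86.8% | 11.18 |

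At the 5% comparator rate, 7.1 points gives 89.5% and 7.2 points gives 90.3%. The incidence with a 95% chance of at least one reaction is 1 − 0.05^(1/495) = 0.603%.

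**The case against.** The strongest reply is that nothing was miscalculated. Every figure reproduces at its stated inputs, and the comparison sentence is conditional on 550 and 275 vaccinated infants. A reader might infer that Table 12.2 is arithmetically wrong. It is not; the fault lies only in carrying the figures over to Dose 2. The conditional wording does not remove that fault, because the same sentence extends the result to each vaccination, in a section that plans for 10% dropout.

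The second reply concerns timing, and it stands. A reader might infer that the Dose 2 comparison simply has 87% power. The documents do not say when dropout occurs: some may fall between the Dose 2 diary and the final visit, and Protocol 7.4 expects loss to be low. The 10% case is therefore an upper bound on planned loss. At 2% loss the comparison still has 90.1%.

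The third reply also stands. The 93.5% is the chance of seeing any event in one arm, not the power of a comparison, and should not be read beside the 87% as if it were.

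The fourth reply limits the importance. SAP 12.2 makes the per-dose tables supportive. In the any-dose table, an infant who leaves after the Dose 1 diary still counts, so 550/275 remains close to right there. Protocol 12.4.2 nevertheless specifies the per-dose comparison under the primary safety objective, so its stated power should still be correct.

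**Conclusion.** The point holds as a minor overstatement confined to Dose 2. The 90% and 95% figures are right for Dose 1 and approximately right for any dose. For Dose 2 the plan gives no allowance for its own dropout assumption. Power for the 6.8-point difference then lies between 90.8% with no loss and about 87% with all planned loss before the diary; the detection probability lies between 95.2% and about 93.5%. In the worst planned case the detectable difference moves from 6.8 to about 7.2 points, and the detectable incidence from 0.55% to about 0.60%.

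These ranges assume equal proportional loss in both arms and usable Dose 2 diary data from every infant who remains. A reader might infer that the trial is too small for its safety objective. The documents do not support that: enrollment was set by the 500-recipient requirement, and no safety success threshold depends on the 6.8 points.

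**What to change.** In Protocol 12.2 (text and Table 12.2) and SAP section 5:

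1. Limit the existing 550/275 statements to Dose 1 and any dose.
2. Add a Dose 2 line at 495/248, labelled as assuming that all planned dropout occurs before the Dose 2 diary: 90% power for about a 7.2-point difference at a 5% comparator rate, and a 95% chance of at least one reaction at about 0.60% incidence.
3. If the whole table is restated for Dose 2, the six differences, to one decimal, are 4.4, 5.4, 7.2, 9.0, 10.3 and 11.2 points.

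The cost is editorial. Sample size, analysis and conduct do not change; the stated sensitivity for Dose 2 becomes slightly less favorable.
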